4.2 Study size

Due to the descriptive design of the proposed non-interventional study, a formal sample size calculation has not been performed based on statistical power and protection for type I error.

In previously published studies in Spain (Miravittles, 2015), 66% of patients in usual clinical practice attending to primary care are non-exacerbators and of these, 61% are treated with ICS, therefore approximately 40% of all patients are currently treated with ICS without having exacerbations in the prior year.

Assuming a sample size of 900 patients and 40% of the patients are treated with ICS at the study visit and did not have a moderate or severe COPD exacerbation in the prior year, the 95% confidence interval for this proportion would be between 36.8% (lower limit) and 43.2% (upper limit). To

Document: \\bcnfs02\general\Hdmgener\MEDICAL AFFAIRS 28.02.2017 actualizada\8. SRO ESTUDIOS\RESPIRATORIO\1237-0070 NIS OPTI\11 - Clinical Trial Report\SAP\SAP - V 1.0\SAP OPTI version1.0 29052019.docx

Author:

Version Number: 1.0

Version Date: [29MAY2019]

Template No.: RWI_TP_BIOS0013 Revision 1

Reference: RWI_WI_BIOS0015

Effective Date: 15Jun2018

Copyright © 2018 All rights reserved. The contents of this document are confidential and proprietary to subsidiaries. Unauthorized use, disclosure or reproduction is strictly prohibited.

Holdings Inc. and its

account for a 10% drop-out rate (patients with inconsistent, incomplete or missing data), the sample size becomes 1,000 patients.

Table 1. Scenario for estimated proportions by 95% confidence intervals (95% CI)

	1	2	3	4	5	6	7	8
Expected proportion	0.4				0.5			
Lower and Upper limit of 95% CI	(0.37;0.43)	(0.368;0.432)	(0.365;0.435)	(0.363;0.437)	(0.47;0.53)	(0.468;0.532)	(0.465;0.535)	(0.463;0.537)
Precision of estimation	0.030	0.032	0.035	0.037	0.030	0.032	0.035	0.037
N (at final analysis)	1000	900	753	674	1042	938	784	702
Dropout 10%	1112	1000	838	749	1159	1043	872	780

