7.2.10 COTE Index

The COTE comorbidity index was constructed from the 12 comorbidities that were associated with a statistically significant risk of death (Divo et al. 2012). Thus, comorbidities such as hypertension and hypercholesterolemia, which are very frequent in patients with COPD, would not be associated with higher mortality, while others would be, such as cancer (particularly lung, esophagus, pancreas and breast), anxiety, liver cirrhosis, atrial fibrillation, diabetes, pulmonary fibrosis, heart failure, gastroduodenal ulcer and coronary heart disease.

The sum of the points aims to capture the individual or combination of diseases that affect each patient. The total score ranges between 0 and 25 points. An increase of 1 point in the COTE index is associated with an increased risk of death from episodes related to COPD and not related to COPD.

Document: \\bcnfs02\general\Hdmgener\MEDICAL AFFAIRS 28.02.2017 actualizada\8. SRO ESTUDIOS\RESPIRATORIO\1237-0070 NIS OPTI\11 - Clinical Trial Report\SAP\SAP - V 1.0\SAP OPTI version1.0 29052019.docx

Author: _____ Version Number: 1.0
 Version Date: [29MAY2019]

Template No.: RWI_TP_BIOS0013 Revision 1 Reference: RWI_WI_BIOS0015

Effective Date: 15Jun2018

Table B: Comorbidities associated with mortality and the COTE index

Disease	Points
Lung, esophagus, pancreas or breast cancer	6
Pulmonary fibrosis	2
Auricular Fibrillation / flutter	2
Congestive heart failure	1
Coronary artery disease	1
Gastroduodenal ulcer	1
Liver cirrhosis	2
Diabetic neuropathy	2
Anxiety	6
All other cancers	2
Total score	∑ (sum of all points)

The COTE index will also be described according to the mortality risk at this cut-off point:

- Low risk mortality: COTE index <4 points
- High risk mortality: COTE index ≥ 4 points.

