8.2 Statistical Tests and Confidence Intervals

Unless otherwise specified in the description of the analyses, a two-sided 95% confidence interval will be considered as a default ($\alpha = 5\%$). P-values are provided as descriptive representations of the data, since no confirmatory testing is planned.

Document: \\bcnfs02\general\Hdmgener\MEDICAL AFFAIRS 28.02.2017 actualizada\8. SRO ESTUDIOS\RESPIRATORIO\1237-0070 NIS OPTI\11 - Clinical Trial Report\SAP\SAP - V 1.0\SAP OPTI version1.0 29052019.docx

Author:

Version Number: 1.0

Version Date: [29MAY2019]

Template No.: RWI_TP_BIOS0013 Revision 1

Reference: RWI_WI_BIOS0015

Effective Date: 15Jun2018

Copyright © 2018 All rights reserved. The contents of this document are confidential and proprietary to Holdings Inc. and its subsidiaries. Unauthorized use, disclosure or reproduction is strictly prohibited.

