16.1.3.1 Current treatment with ICS

Main variable will be presented according to the presence or not of moderate/severe exacerbations in the previous 365 days.

The use of ICS will be analyzed using number of patients in each category and percentages (absolute and relative frequencies) and 95% confidence intervals will be provided based on Wald's (Normal Approximation) method for each group. Percentages will be compared using Chi-Square test or Fisher's Exact test.

Logistic regression will be used to assess the independent contribution of clinical and demographic factors to the estimation of the proportion of patients with COPD who use ICS inadequately. First, univariate and second, multiple logistic regression (MLR) methods will be used to investigate the impact of the following explanatory covariates (patient and disease characteristics) on ICS use.

Potential covariates are:

- Age
- gender
- Smoking history
- Number of exacerbations in the previous year.
- History of asthma (yes/no)
- History of atopy (yes/no)
- COTE index
- COPD GesEPOC 2017 phenotype

Document: \\bcnfs02\general\Hdmgener\MEDICAL AFFAIRS 28.02.2017 actualizada\8. SRO ESTUDIOS\RESPIRATORIO\1237-0070 NIS OPTI\11 - Clinical Trial Report\SAP\SAP - V 1.0\SAP OPTI version1.0 29052019.docx

Author:

Version Number: 1.0

Version Date: [29MAY2019]

Template No.: RWI_TP_BIOS0013 Revision 1

Reference: RWI_WI_BIOS0015

Effective Date: 15Jun2018

Copyright © 2018 All rights reserved. The contents of this document are confidential and proprietary to Holdings Inc. and its subsidiaries. Unauthorized use, disclosure or reproduction is strictly prohibited.

- GOLD 2019 spirometric classifications (1, 2,3, 4)
- GOLD 2019 patient groups (A, B, C, D)
- mMRC score
- CAT - COPD Assessment Test

Backward selection procedures will be applied to generate the final MLR models which consider only covariates in the selection procedure with a p-value <0.1 in the corresponding univariate logistic regression analysis, using inadequate ICS use (yes/no) as response variable. A p-value <0.05 will be used for the covariates to stay in the model in a backward elimination step. Continuous variables can be replaced by categorical variables. Parameters estimated, exp(B) and C95% Wald Confidence Limits for OR will be presented.

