20.3 Endpoints

20.3.1 ICS treatment

Table 24. Current treatment on ICS according to the absence or presence of moderate/severe exacerbations in the year prior to the study visit.

ICS treatment	Moderate/severe Exacerbations in the previous year		Total
	No	Yes	
Total patients	N (100%)	N (100%)	N (100%)
Currently non treated with ICS	XXX (XX.X%) [95%CI: XX.X%-XX.X]	XXX (XX.X%) [95%CI: XX.X%-XX.X]	XXX (XX.X%) [95%CI: XX.X%-XX.X]
Currently treated with ICS	XXX (XX.X%) [95%CI: XX.X%-XX.X]	XXX (XX.X%) [95%CI: XX.X%-XX.X]	XXX (XX.X%) [95%CI: XX.X%-XX.X]

*Note: Percentages will be column percentages. Each percentage will correspond to percentage of patients currently treated with ICS, according to the presence of moderate/severe exacerbations in the previous year.

Table 25. Inadequate use of ICS (use of ICS without moderate/severe exacerbations in the previous year) according to clinical and demographic factors (univariate logistic regression analysis)

Variable	Category	Inadequate use of ICS	Odds-Ratio (OR)	p-value
Age	Cont (1 year)	n/N (%)		
Age (cat)	40-49 years	n/N (%)	(ref)	
	50-59 years	n/N (%)		
	60-69 years	n/N (%)		
	70-79 years	n/N (%)		
	80+ years	n/N (%)		

Document: \\bcnfs02\general\Hdmgener\MEDICAL AFFAIRS 28.02.2017 actualizada\8. SRO ESTUDIOS\RESPIRATORIO\1237-0070 NIS OPTI\11 - Clinical Trial Report\SAP\SAP - V 1.0\SAP OPTI version1.0 29052019.docx

Author:

Version Number: 1.0

Version Date: [29MAY2019]

Template No.: RWI_TP_BIOS0013 Revision 1

Reference: RWI_WI_BIOS0015

Effective Date: 15Jun2018

Copyright © 2018 All rights reserved. The contents of this document are confidential and proprietary to Holdings Inc. and its subsidiaries. Unauthorized use, disclosure or reproduction is strictly prohibited.

Variable	Category	Inadequate use of ICS	Odds-Ratio (OR)	p-value
Gender	Male Female		(ref)	
BMI cat	Underweight: BMI< 18.5 kg/m ² Normal weight: 18.5 kg/m ² ≤ BMI≤ 25 kg/m ² Overweight: 25 kg/m ² < BMI≤ 30 kg/m ² Obese: 30 kg/m ² <BMI≤ 35 kg/m ² Severely Obese: BMI> 35 kg/m ²		(ref)	
Smoking habit	Non-smoker Smoker Ex-smoker		(ref)	
History of asthma	No Yes		(ref)	
History of atopy	No Yes		(ref)	
BODEx Index (cat)	Class I Mild: BODEx 0-2 points Class II Moderate: BODEx 3-4 points Class III Serious: BODEx 5-6 points Class IV Very serious: BODEx 7-9 points		(ref)	
COTE Index (cat)	Low risk: COTE index <4 points High risk: COTE index ≥ 4 points.		(ref)	
Time since COPD diagnosis (cat)	0-2 years >2-5 years >5 years		(ref)	

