COPD GesEPOC 2017 phenotypes	non-exacerbator, mixed COPD - asthma syndrome (ACOS), exacerbator with emphysema exacerbator with chronic bronchitis		(ref)	
GOLD 2019 spirometric classification	Gold 1 – Mild Gold 2 – Moderate Gold 3 – Severe Gold 4 – Very severe		(ref)	
GOLD 2019 patient groups (A, B, C, D)	Patient A Patient B Patient C Patient D		(ref)	
CAT score (cat)	CAT <10: Low impact of COPD. CAT ≥10: Medium / high impact of COPD		(ref)	
mMRC score	Grade 0 Grade 1 Grade 2 Grade 3 Grade 4		(ref)	
Number of eosinophils (%)	<2% ≥ 2%		(ref)	

Document: \\bcnfs02\general\Hdmgener\MEDICAL AFFAIRS 28.02.2017 actualizada\8. SRO ESTUDIOS\RESPIRATORIO\1237-0070 NIS OPTI\11 - Clinical Trial Report\SAP\SAP - V 1.0\SAP OPTI version1.0 29052019.docx

Author:

Version Number: 1.0

Version Date: [29MAY2019]

Template No.: RWI_TP_BIOS0013 Revision 1

Reference: RWI_WI_BIOS0015

Effective Date: 15Jun2018

Copyright © 2018 All rights reserved. The contents of this document are confidential and proprietary to Holdings Inc. and its subsidiaries. Unauthorized use, disclosure or reproduction is strictly prohibited.

Variable	Category	Inadequate use of ICS	Odds-Ratio (OR)	p-value
Inmunoglobulin E (UI/ml)	<= 100 UI/ml >100 UI/ml		(ref)	
Presence of exacerbations in previous 2 years	None 1-2 exacerbations 3-4 exacerbations 5+ exacerbations		(ref)	
Presence of moderate/severe exacerbations in previous 2 years	None 1-2 moderate/severe exacerbations 3-4 moderate/severe exacerbations 5+ moderate/severe exacerbations		(ref)	
Presence of severe exacerbations in previous 2 years	None 1-2 severe exacerbations 3-4 severe exacerbations 5+ severe exacerbations		(ref)	
Presence of exacerbations in previous year	None 1-2 exacerbations 3-4 exacerbations 5+ exacerbations		(ref)	
Presence of moderate/severe exacerbations in previous year	None 1-2 moderate/severe exacerbations 3-4 moderate/severe exacerbations 5+ moderate/severe exacerbations		(ref)	
Presence of severe exacerbations in previous year	None 1-2 severe exacerbations 3-4 severe exacerbations 5+ severe exacerbations		(ref)	
Antibiotics for COPD exacerbations	No Yes		(ref)	
Oral corticosteroids for COPD exacerbations	No Yes		(ref)	
Type of ICS	ICS alone LABA + ICS LABA + LAMA + ICS			

Inadequate use of ICS: use of ICS without moderate/severe exacerbations in the previous year in patients.

Table 26. Multivariate logistic regression model of inadequate use of ICS (use of ICS without moderate/severe exacerbations in the previous year)

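### The inadequate-ICS-use regression does not fix the scale of CAT and COTE: Table 25 screens them only as two classes, and the text allows continuous variables to be recoded without a rule

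*SAP*

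**What the plan says.** SAP 16.1.3.1 models inadequate ICS use by logistic regression. Covariates with a univariate p<0.1 go forward, and backward elimination keeps those with p<0.05. CAT and the COTE index are both on the candidate list, with no form stated. The paragraph on selection then adds: "Continuous variables can be replaced by categorical variables". Section 16.2.2 repeats that sentence for the negative binomial models of exacerbation counts.

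The form appears in three other places, which do not agree:
- Table 25 (SAP 20.3.1), the univariate logistic shell, has only two classes for CAT, "CAT <10: Low impact of COPD. CAT ≥10: Medium / high impact of COPD", and two for COTE, "Low risk: COTE index <4 points High risk: COTE index ≥ 4 points". Age is the only variable with a per-unit row, and it also has a five-group row.
- SAP 8.3 lists CAT as a category and does not list COTE.
- Protocol 9.3.3 names the CAT itself as an independent variable for the multivariable analysis.

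Both scores exist as numbers. CAT runs from 0 to 40 (SAP 7.2.13) and COTE from 0 to 25 (SAP 7.2.10), and Tables 8 and 9 summarise them with means and medians. The COTE cut is introduced for description: "The COTE index will also be described according to the mortality risk at this cut-off point". The CAT cut at 10 also forms part of the GOLD A-D grouping (SAP 7.2.12), a separate candidate in the same model.

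**The concern.** The regression is meant to show which factors contribute independently to inadequate ICS use. A two-class CAT treats a score of 10 and a score of 40 as the same patient. If the relation is graded, this discards information at both the p<0.1 screen and the p<0.05 retention step. It also leaves part of the CAT or COTE effect unadjusted in the other odds ratios.

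The recoding sentence raises a different problem. It names no variable, trigger, cut or timing. Two analysts following the SAP could fit different models, and one who tries both scales and keeps the more significant has a selection error above the nominal level. What is at stake is the reliability of the list of reported factors.

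**Working it through.** **Plan's own figures.** The plan states "Assuming a sample size of 900 patients and 40% of the patients are treated with ICS at the study visit" with no moderate or severe exacerbation in the prior year. The half-width is 1.96 × √(0.40 × 0.60 / 900) = 0.0320, so the interval is 36.8% to 43.2%, as stated. The 10% allowance gives 900 / 0.9 = 1,000, as stated. These size a proportion; the SAP gives no size or power for the regression.

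**Size of the regression sample.** Of the patients, 66% "are non-exacerbators and of these, 61% are treated with ICS". So 900 × 0.66 = 594 patients without exacerbations, of whom 594 × 0.61 ≈ 362 are on ICS. SAP 16.1.3.2 restricts the inadequate-use analysis to patients without exacerbations, so I use N = 594 with a 61% outcome.

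**Assumptions.** The documents give no effect size, no score distribution and no share above each cut. I assume an odds ratio of 1.25 per SD, log-linear, and vary the cut.

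**Reading A: the two-class coding governs.**

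1. Continuous predictor. Expected z = ln(1.25) × √(594 × 0.61 × 0.39) = 0.2231 × 11.89 = 2.65. Power at two-sided 0.05 = Φ(2.65 − 1.96) ≈ 76%.
2. Normal predictor cut in two, with a share q on one side. The fraction of information kept is φ(c)² / [q(1 − q)], where c is the cut, and z shrinks by its square root.

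| Smaller class | Information kept | z | Power, formula | Power, simulation |
|---|---|---|---|---|
| none (continuous) | 100% | 2.65 | 76% | 74-75% |
| 50% | 64% | 2.12 | 56% | 55-56% |
| 30% | 58% | 2.01 | 52% | 51% |
| 20% | 49% | 1.86 | 46% | about 47% |

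The simulated loss is about 19 to 28 points; the formula gives 19 to 30. At the p<0.1 screen, simulated power is 83-84% continuous against 60-69% cut.

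3. COTE is not normal. Its weights are only 1, 2 and 6, so a cut at 4 mostly picks out patients with a 6-point condition. For a score built from those weights (assumed independent prevalences of 2-12%, giving 17% at or above 4), score and cut correlate at 0.90. Information kept is 0.90² = 81%, z = 2.65 × 0.90 = 2.39, and power by formula is 67% against 76%. Simulation gives 63% against 72%. The loss is about 9 points either way.

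4. If the truth is a step at the cut, the result reverses. For a normal predictor with an assumed step odds ratio of 1.6 and 20 / 30 / 50% below the cut, simulated power is 62 / 74 / 80% for the cut and 36 / 52 / 60% for the continuous term. For the COTE-like score with a step odds ratio of 1.7, it is 61% for the cut and 53% for the score.

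**Reading B: the recoding sentence governs.** For a factor with no effect, one fixed coding is selected 5% of the time (10% at the screen). If the more significant of the continuous and two-class forms is taken, simulation gives about 7 to 9% (about 14 to 17% at the screen). The two tests are strongly correlated, so the rate does not double.

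**The case against.** Several points on the other side stand.

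- **The two costs are alternatives.** If Table 25 governs, CAT and COTE have one coding each and there is no selection inflation. If the 16.1.3.1 list and the recoding sentence govern, dichotomising is not forced. The losses must not be added together.
- **The cuts are pre-specified.** They are fixed in SAP 7.2.10 and 7.2.13, so cutting alone does not raise false selection; only the open recoding does. A reader might infer that analysts will choose the scale after seeing the data. The SAP does not say so. The inference rests on the missing rule and on a SAP date of 29 May 2019, after the planned April 2019 end of data collection.
- **The outcome reflects prescribing.** Prescribers may act on guideline thresholds, so a step at CAT 10 is plausible, and the cut would then be the better form. The documents do not settle the shape, so it would be too strong to say that real factors are missed.
- **Eosinophils and IgE.** Table 25 cuts these in two as well, and a reader might count them among the dichotomised model predictors. They are in neither the 16.1.3.1 nor the 8.3 list. Table 25 carries other rows outside those lists, so it may simply be a broader univariate table. BODEx is likewise a Table 25 row outside both SAP lists, although Protocol 9.3.3 names it for the multivariable analysis.
- **Age is a weak example of selection by scale.** It is the one variable shown both ways, but 8.3 makes it a fixed variable.
- **The analysis is not confirmatory.** SAP 8.2 states: "P-values are provided as descriptive representations of the data, since no confirmatory testing is planned". The count models in 16.2.2 are labelled exploratory.

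These points limit the size and reach of the concern. They do not remove the disagreement over the form of CAT or supply the missing rule.

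**Conclusion.** The concern holds in a limited form. The SAP does not fix one scale for CAT and COTE in the inadequate-use regression: the covariate list, 8.3 and Table 25 differ, and the recoding sentence has no criterion.

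On one reading, power at p<0.05 falls by about 19 to 28 points if the score is normal, as CAT might be, and by about 9 points for a score shaped by the COTE weights. Both figures assume N = 594, a log-linear effect and an odds ratio of 1.25 per SD; the first assumes 20 to 50% of patients below the cut, the second the assumed prevalences. A true step at the cut would favour the cut. On the other reading, a null factor is selected about 7 to 9% of the time instead of 5%, and passes the screen about 14 to 17% of the time instead of 10%.

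This affects how far the reported factors can be trusted. It does not touch the primary proportion or its confidence interval. The change is worth making because it is cheap and the regression is placed under the primary analysis.

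**What to change.** Before the analysis is run:

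1. In SAP 16.1.3.1, 16.2.2, 8.3 and Table 25, enter the CAT and COTE scores as continuous terms, with an odds ratio (or rate ratio in 16.2.2) per stated unit, for example per 5 CAT points. Age already has a per-unit row.
2. Pre-specify one non-linearity check, such as a quadratic term or a restricted cubic spline. It matters most for COTE, whose weights make it lumpy.
3. In 16.1.3.1 and 16.2.2, delete the recoding sentence or replace it with a rule that does not depend on p-values.
4. Keep the clinical cuts in Table 25 as descriptive n/N (%) rows outside the p<0.1 screen.
5. State whether eosinophils, IgE and BODEx are model candidates, reconciling Table 25, the SAP lists and Protocol 9.3.3. If they are, give each one pre-stated form.

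The cost is SAP wording and the layout of one table; no new data are needed. The downside is small: per-unit odds ratios are less familiar to clinicians than a two-class contrast, and linearity has to be checked.

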Additionally, logistic regression model will be performed for each age subgroup, using the same procedure described in the previous paragraph. Age subgroups will be adjusted according to the distribution of patients.

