Parameter	Cat	DF	Estimate	Standard Error	Wald Chi-Square	Pr > ChiSq	Exp(Est)
Intercept							

Document: \\bcnfs02\general\Hdmgener\MEDICAL AFFAIRS 28.02.2017 actualizada\8. SRO ESTUDIOS\RESPIRATORIO\1237-0070 NIS OPTI\11 - Clinical Trial Report\SAP\SAP - V 1.0\SAP OPTI version1.0 29052019.docx

Author:

Version Number: 1.0

Version Date: [29MAY2019]

Template No.: RWI_TP_BIOS0013 Revision 1

Reference: RWI_WI_BIOS0015

Effective Date: 15Jun2018

Parameter	Cat	DF	Estimate	Standard Error	Wald Chi-Square	Pr > ChiSq	Exp(Est)
Variable 1							
Variable 2	Cat 2 Cat 3 Cat 4						
...							
Variable n							

Effect	OR Point Estimate	95% Wald Confidence Limits
Variable 1		
Variable 2		
...		
Variable n		

Table 27. Multivariate logistic regression model of inadequate use of ICS (use of ICS without moderate/severe exacerbations in the previous year) by age subgroups

Effect	Patients aged ≤ xx years		Patients aged xx- xx years				Patients aged > xx years	
	OR (95% CI)	p-value	OR (95% CI)	OR (95% CI)	OR (95% CI)	p-value	OR (95% CI)	p-value
Variable 1								
Variable 2								
...								
Variable n								

Document: \\bcnfs02\general\Hdmgener\MEDICAL AFFAIRS 28.02.2017 actualizada\8. SRO ESTUDIOS\RESPIRATORIO\1237-0070 NIS OPTI\11 - Clinical Trial Report\SAP\SAP - V 1.0\SAP OPTI version1.0 29052019.docx

Author: Version Number: 1.0
Version Date: [29MAY2019]

Template No.: RWI_TP_BIOS0013 Revision 1 Reference: RWI_WI_BIOS0015

Effective Date: 15Jun2018

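### Repeating backward selection within each age subgroup leaves the odds ratios in SAP Table 27 not comparable across columns, and the selected predictors will very probably differ even where age changes nothing

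*SAP*

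**What the plan says.** SAP 16.1.3.1 models inadequate ICS use by logistic regression and lists 12 candidates under "Potential covariates are". On selection it states: "Backward selection procedures will be applied to generate the final MLR models". The procedure is to "consider only covariates in the selection procedure with a p-value <0.1 in the corresponding univariate logistic regression analysis", and then: "A p-value <0.05 will be used for the covariates to stay in the model in a backward elimination step".

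The section adds that a "logistic regression model will be performed for each age subgroup, using the same procedure described in the previous paragraph", and on the groups themselves: "Age subgroups will be adjusted according to the distribution of patients". The output is Table 27, "Multivariate logistic regression model of inadequate use of ICS (use of ICS without moderate/severe exacerbations in the previous year) by age subgroups". Its shell appears to have three age blocks with odds ratios and p-values, and every cut-point is a placeholder, as in "Patients aged > xx years".

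Neither document plans an age-by-covariate interaction, a covariate set common to all ages, or a rule for reading differences between columns. Protocol 9.7.2 plans logistic regression but no age-subgroup models. Tables 6 and 25 already use five fixed age bands (40-49, 50-59, 60-69, 70-79, 80+).

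**The concern.** Selection is redone within each age group rather than one model being refitted. Two problems follow.

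- Where the retained sets differ, the odds ratio for a given variable is adjusted for different covariates in each column, so the columns cannot be compared directly.
- A variable kept in one column and dropped from the next invites the reading that it matters at one age and not another. Nothing in the plan estimates that contrast. A p-value on either side of 0.05 in two small subgroups is weak evidence of a difference between them.

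At stake is whether Table 27 carries usable information about age or mainly shows the instability of stepwise selection in small samples.

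**Working it through.** **1. The plan's own figure.** SAP 4.2 and Protocol 9.5 assume 40% in 900 patients. 0.40 ± 1.96 × √(0.40 × 0.60 / 900) = 0.40 ± 0.032, that is 36.8% to 43.2%, and 900 / 0.9 = 1,000. Both match. No figure is given for the subgroup models.

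**2. Cohort.** The SAP supports two readings.
- Exacerbation-free (16.1.3.2): 0.66 × 900 = 594 patients, of whom 0.61 × 594 ≈ 362 are on ICS and about 232 are not.
- Full analysis set (16.1.3): 900 patients, of whom 0.40 × 900 = 360 are inadequate users. The candidate list includes the previous year's exacerbation count, and Table 25 has levels of that count above none. Both fit this reading better.

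**3. Parameters.** One each for age, gender, exacerbation count, asthma, atopy, COTE and CAT (7), smoking 2, phenotype 3, GOLD spirometric class 3, GOLD group 3, mMRC 4: 22 in all, taking age, count, COTE and CAT as continuous. Patients in the rarer outcome category per parameter, with equal age thirds assumed:
- Exacerbation-free: 232 / 22 = 10.5 overall and 232 / 3 / 22 = 3.5 per third. The exacerbation count is constant here, and GOLD C and D are empty if judged on the same year, so about 19 parameters remain: 77.3 / 19 = 4.1.
- Full analysis set: 360 / 22 = 16.4 overall and 5.5 per third.

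The range per third is therefore about 3.5 to 5.5.

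**4. Mechanism (illustration).** Ten null candidates in three groups make 30 tests. At 0.05, treated as independent, 1 − 0.95³⁰ = 0.79 is the chance of at least one false entry. For a true odds ratio of 2 (binary covariate, half exposed, 55% against 71%), power is about 65% in 198 patients and 98% in 594. A predictor with that power enters some thirds but not others with probability 1 − 0.645³ − 0.355³ = 0.69.

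**5. Simulation of the planned procedure.** 1,500 runs per scenario; univariate Wald p<0.1 to enter, p<0.05 to stay; true effects identical in every subgroup. There are ten binary candidates (the 12 less age and the exacerbation count) at 50% prevalence, with equal subgroups and no missing data. These settings are assumptions. The table gives the share of runs in which the three selected sets were not all the same.

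| True predictors | N = 594 (61% response) | N = 900 (40% response) |
|---|---|---|
| none | 80% | 78% |
| three, OR 1.5 | 97% | 99% |
| three, OR 2 | 99% | 94% |
| three, OR 2.5 | 92% | not run |
| three, OR 3 | 79% | 62% |
| five, OR 2 | 100% | not run |
| three, OR 2, correlated (latent r = 0.3) | 99% | 94% |

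Eleven of the 12 scenarios give 78% or more. Three-subgroup runs under other assumed covariate distributions gave 96% to 99%. With only two subgroups the range was 45% to 83%.

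**6. The alternative.** One pooled model with pre-specified covariates and one global likelihood-ratio test of age by covariate (10 df, age continuous) was significant at 0.05 in 5.4% to 6.4% of runs (N = 594 or 900; no predictors, or three at OR 2).

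**The case against.** **No stated purpose.** The case for leaving the plan alone is that it never says Table 27 is for comparing ages. No objective or outcome concerns age differences, the protocol's ENCePP checklist marks effect modification as not applicable (item 8.1), SAP 8.2 calls p-values descriptive, and Protocol 9.9 disclaims causal conclusions. This stands in part: a reader might infer that the table is meant to establish effect modification by age, but that comes only from its side-by-side layout. The descriptive label does not cure the problem, because p-values decide which covariates appear at all.

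**Certainty.** A reader might infer that the columns are bound to differ. They are not: with three subgroups and uniformly strong predictors in 900 patients the figure falls to 62%. The text does not fix the number of subgroups, and the shell's middle block is irregular, so three is itself a reading.

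**Cut-points.** Leaving them open might look like tuning to the result. The SAP ties them to the distribution of patients, not to the outcome, so this is a small avoidable freedom and not the source of the problem.

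**Cohort.** Quoting only the exacerbation-free reading would overstate the sparseness, hence the range in step 3. How often any particular predictor survives in all three groups depends heavily on assumptions, so no claim is made about that.

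**Conclusion.** The point holds for Table 27. Selection is repeated by age, the columns have no common adjustment set, and no interaction is estimated. If age changed nothing, the three selected sets would still differ in about 62% to 100% of studies, and about 80% to 100% under most scenarios tried, on either cohort reading. Differences between columns would then mostly reflect selection and low power, with about 3.5 to 5.5 patients in the rarer outcome category per candidate parameter per age third.

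The percentages rest on assumed prevalences, odds ratios, equal subgroups and complete data. Multi-category covariates and incomplete records would lower the power in each subgroup. The 5.4% to 6.4% for the pooled test measures something different (a formal false positive, not differing sets), so the two ranges show the contrast in behaviour and are not a like-for-like error rate.

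It would be wrong to conclude that the study's main result is in doubt. The primary proportion, its confidence interval and the pooled model in Table 26 do not depend on this step. It is a cheap improvement to one supplementary table.

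**What to change.** Amend SAP 16.1.3.1 and the Table 27 shell as follows.

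1. Use one covariate set, that of the pooled final model, in all age groups, with no re-selection.
2. Fit one pooled model with age-group-by-covariate interaction terms.
3. In Table 27 report the age-specific odds ratios from that model with confidence intervals, together with the interaction estimates or a global interaction test.
4. Label the table exploratory.
5. As a minor addition, build the age groups from the bands in Tables 6 and 25, with a rule for merging sparse bands written down before the models are run.

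The cost is SAP wording and less programming than separate selections; no new data are needed. The downside is that a predictor that matters in only one age group will show only through its interaction term, which will be imprecise. Its confidence interval will at least make that visible. The pooled test in step 6 of the working used pre-specified covariates and continuous age, so its exact error rate need not carry over to a selected covariate set with age groups.
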